Alzheimer's family caregivers will be identified through a registry of persons with dementia at the Vietnam National Geriatric Hospital in Hanoi.

Page 1 of 8 Revised: February 27, 2017

To be eligible, the person will be an adult who is the identified primary adult caregiver (i.e. the person spending the most time day-to-day providing care) to an older adult who is living in the community and has received a diagnosis of Alzheimer's disease or another degenerative dementia. All participants will be living in the Soc Son area outside Hanoi, Vietnam.

The final sample will be 50 family caregivers of persons diagnosed with dementia (25 in the active intervention and 25 in the control group). The study will exclude

- Adults unable to consent
- Individuals who are not yet adults (infants, children, teenagers)
- Prisoners
- Pregnant women.

5) Study Timelines

- Each family caregiver will participate in the study for 3 months.
- We will enroll subjects from April 1 through the end of September, 2018.
- We will complete preliminary analysis of the data by the end of January of 2019.

6) Study Endpoints

This is a time-limited intervention lasting up to 3 months.

7) Procedures Involved

This is cluster randomized controlled trial to pilot-test a culturally adapted behavioral intervention to support Alzheimer's family caregivers.

Participants in the intervention clusters will receive a manualized intervention that will consist of 3-6 one-hour sessions with a trained health professional (e.g. nurse, social worker, or physician) who has been certified to deliver the intervention. The sessions will be administered in the home (or other setting of the subject's choice such as a clinic) and include several components, including psychoeducation, stress reduction, skill-building. The intervention will be tailored to the needs and preferences of the caregiver.

Participants in the control clusters will receive education about Alzheimer's disease including written informational materials at the time of enrollment (i.e., 1 session).

Participants in both clusters will also be assessed at baseline and at the end of the intervention. These assessments will occur at baselineand 3 months to and will assess primary and secondary outcomes using standardized instruments (i.e., items embedded in Risk Priority Intake Assessment).

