A research protocol will be used that includes scripts, study scales detailed descriptions of the goals for each session, and standardized forms (see attached study manual).

Page 2 of 8 Revised: February 27, 2017

8) Data and/or Specimen Management and Confidentiality

The primary study outcomes are burden of caregiving (Zarit Burden Inventory) and caregiver distress (PHQ-4), found on pages (RP)4 and (RP)5 of the REACH Interventionist Notebook respectively. Secondary outcomes include Alzheimer's disease knowledge (Alzheimer's knowledge scale)

Procedures for maintenance and confidentiality include 1) assigning each participant a unique identifier, 2) data collected will be labeled using the unique identifier and will be stored separately from the key linking personal information (e.g. name, date of birth, address, phone number) and identifiers, 3) all data will be kept under lock and key or on a secure server that is only accessible to research staff, 4) at the conclusion of the study, the key linking identifiers and personal information will be destroyed, 5) all research personnel in the US who have access to the patient data will receive training on conducting human research (e.g. NIH online course) – all investigators in Vietnam will participate in the local equivalent of this training.

9) Data and/or Specimen Banking

All data will be stored on a secure server at in Vietnam. De-identified data will be transferred to UC Davis and the University of South Carolina electronically through an encrypted zip file. After the study, the key linking personal identifiers to the survey data will be destroyed.

10) Provisions to Monitor the Data to Ensure the Safety of Subjects

The goal of this randomized controlled trial care is to assess feasibility, acceptability, and preliminary effectiveness of the behavioral intervention to support Alzheimer's family caregivers. Case review will occur on a weekly basis with a team that includes the care manager and the local PI and one investigators from the UC Davis and the U of SC. The caregiver's level of distress and any indicators of elder abuse/neglect will be reviewed at each session.

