Cases of potential elder abuse/neglect and caregiver suicidal ideation will be handled according to study protocols that are consistent with local practice in Vietnam. Field staff will report all suspected cases of elder abuse/neglect within 24 hours to study investigators [name] (neurologist) and [name] (a geriatrician) at the National Geriatric Hospital. After consultation with the research team including Drs. [name] (a geriatric psychiatrist) and [name] (a social worker), [name] may take additional steps, including contacting and directly assessing the situation, educating family members about abuse, and referring families to local services (e.g. temples, elder clubs, social work services) for counseling and support. Similarly, field staff will report to [name] any caregivers who express suicidal ideation. [name] will then directly contact and assess the caregiver and determine if additional steps are necessary, including referring the caregiver for counseling, support and/or hospital-based mental health and social services. Field staff, usually nurses or social workers, will be trained in these written protocols by the study staff (i.e. [name] and [name]). All cases of elder abuse and caregiver suicidal ideation will be treated as adverse events and discussed at monthly research meetings and reported to each institution's IRB. [name] will report serious adverse events to the SO and NIA.

11) Withdrawal of Subjects

Subjects (patients and family members) may withdraw at any time. If they withdraw from the study, they will be given the option of having their records destroyed.

Page 4 of 8 Revised: February 27, 2017

12) Risks to Subjects

There are two main risks associated with this study: 1) discomfort or mild distress because of the intervention and 2) inconvenience because of the need to fill out the study questionnaires. These risks are similar to the risk of undergoing routine assessments in healthcare clinics in Vietnam. Specific steps are being taken to address each category of risk.

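### Safety review is scheduled by session (3-6 versus 1) with no stated query common to both arms, so events are less likely to be detected in controls and raw by-arm counts would not be comparable

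*Protocol*

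**What the plan says.** **When safety is reviewed.** Protocol section 10 states that "any indicators of elder abuse/neglect will be reviewed at each session", and has caregiver distress reviewed on the same occasions. It does not define a session by arm.

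**How many sessions.** Under section 7 the intervention clusters receive a "manualized intervention that will consist of 3-6 one-hour sessions with a trained health professional". The control clusters receive education, with "written informational materials at the time of enrollment (i.e., 1 session", so one session in total.

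**Assessments.** Section 7 adds: "Participants in both clusters will also be assessed at baseline and at the end of the intervention". The time points are baseline and 3 months, and the stated purpose is to measure the primary and secondary outcomes. Section 8 names these as the Zarit Burden Inventory, the PHQ-4 for distress, and Alzheimer's knowledge.

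**What counts as an event.** Section 10: "All cases of elder abuse and caregiver suicidal ideation will be treated as adverse events". The same section has field staff report every suspected case of abuse or neglect within 24 hours, and any caregiver who expresses suicidal ideation. It has adverse events collected in general, and has the team grade incident events for seriousness and likely relationship to the intervention. None of these duties is limited to one arm.

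**Analysis.** The SAP does not mention adverse events, and neither document describes a safety comparison between arms.

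**The concern.** Abuse and suicidal ideation usually come to light because someone is in contact with the family and asks or observes. The plan ties its stated review to sessions, and the number of sessions is part of what differs between the arms. The arm with more sessions has more chances to find the same problem.

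Two things are at stake. The first is participant protection: a control caregiver has no scheduled session after enrollment in a 3-month follow-up, and the visible text puts no abuse or suicidal-ideation question in the one later contact. The second is interpretation. Events are graded for their relationship to the intervention, and that grading bears on expedited reporting of serious events. If anyone looks to the control arm for a background rate, that arm has been observed less. An excess in the intervention arm could then arise with no true difference.

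**Working it through.** The plan gives no adverse-event rate or detection figure, so there is nothing of its own to reproduce. The check counts scheduled contacts and then illustrates what the counts imply.

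**Inputs from the protocol:** sessions, 3-6 versus 1 (section 7); assessments, 2 in each arm (section 7); 25 caregivers per arm (section 4).

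**Step 1: contacts per caregiver.**
- Sessions only: 3-6 versus 1, a ratio of 3 to 6. Over 25 caregivers per arm this is 75-150 versus 25 sessions.
- Sessions plus both assessments: 3 + 2 = 5 to 6 + 2 = 8, versus 1 + 2 = 3. The ratio is 5/3 = 1.7 to 8/3 = 2.7.
- After enrollment: 3 + 1 = 4 to 6 + 1 = 7 if all intervention sessions follow enrollment, versus 0 + 1 = 1.

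**Step 2: chance of at least one detection.** With per-contact probability p and k contacts, detection = 1 - (1 - p)^k. Here p is assumed. The formula also assumes equal true risk in both arms, independent contacts, and a problem that is present and detectable at every contact counted.

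At p = 0.2, sessions only:
- intervention: 1 - 0.8^3 = 0.488 to 1 - 0.8^6 = 0.738
- control: 1 - 0.8^1 = 0.200
- ratio: 0.488/0.200 = 2.4 to 0.738/0.200 = 3.7

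At p = 0.2, with assessments counted:
- intervention: 1 - 0.8^5 = 0.672 to 1 - 0.8^8 = 0.832
- control: 1 - 0.8^3 = 0.488
- ratio: 0.672/0.488 = 1.4 to 0.832/0.488 = 1.7

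**Step 3: range over p.**

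| Assumed p | Sessions only: intervention vs control | Ratio | With assessments: intervention vs control | Ratio |
|---|---|---|---|---|
| 0.1 | 27-47% vs 10% | 2.7-4.7 | 41-57% vs 27% | 1.5-2.1 |
| 0.2 | 49-74% vs 20% | 2.4-3.7 | 67-83% vs 49% | 1.4-1.7 |
| 0.5 | 88-98% vs 50% | 1.8-2.0 | 97-100% vs 88% | 1.1 |
| 0.8 | 99-100% vs 80% | 1.2-1.25 | 99.97-100% vs 99% | 1.01 |

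The direction is the same throughout: more events found in the intervention arm. The size runs from negligible to several-fold, depending on p and on whether the assessments detect anything. The sessions-only columns follow the stated review point. The other columns suppose that the assessments detect safety problems too, which the visible text does not say. Baseline contacts cannot find a problem that arises later, so for new events the after-enrollment count (4-7 versus 1) is the more relevant one.

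**Step 4: scale in events.** If 10% of caregivers in each arm truly had a problem (assumed), that is 25 x 0.10 = 2.5 per arm. With p = 0.2 and sessions only, the expected number found is 2.5 x 0.200 = 0.5 in control and 2.5 x 0.488 = 1.2 to 2.5 x 0.738 = 1.8 in intervention. Counts this small are easily misread.

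**The case against.** The strongest reply is that a reader could go well past the text here. Four tempting inferences are not supported.

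- **That distress and abuse are reviewed only at intervention sessions.** The protocol does not say so. The control contact is itself called a session, so the rule can cover it, and the PHQ-4 measures distress in both arms at baseline and 3 months.
- **That control-arm events go undetected.** Adverse-event collection, 24-hour reporting of suspected abuse, reporting of suicidal ideation and weekly case review carry no arm limit, and controls do have a 3-month contact. Less likely to be detected is as far as the text goes.
- **That a planned safety comparison is biased.** None is planned. Relatedness is graded event by event, so an effect on that grading is possible but not shown.
- **That no common safety query exists.** The study manual, the Risk Priority Intake Assessment and the written abuse and suicidal-ideation procedures are referred to but not available here. Any of them might contain one.

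It can also be said that closer contact in the intervention arm suits the risk that section 12 names first, discomfort from the intervention itself, and that this is a minimal-risk study of 50 caregivers.

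All of this limits the claim, but the core remains. The arm-neutral duties govern what happens once a problem is known or suspected; they set no schedule for finding one. Measuring the PHQ-4 as an outcome is not the same as asking about abuse or suicidal ideation, and the protocol does not say that 3-month scores are reviewed for safety.

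**Conclusion.** The point holds in a limited form. Followed as written, the visible plan gives unequal ascertainment: review is scheduled at 3-6 sessions in one arm and one session, at enrollment, in the other, with no common safety query stated. Events are less likely to be detected in control caregivers, and raw by-arm counts would not be comparable if reported or used as a background rate.

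The contact counts come from the protocol. The detection ratios do not: they rest on an assumed p and on the assumptions in step 2 of the working, and should be read as illustration. The conclusion also depends on the unseen manual and instruments containing no common query; if they do contain one, what remains is a gap in the protocol text. The efficacy analysis is not affected. This is an inexpensive improvement worth making, not a fault that undermines the trial.

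**What to change.** 1. In section 10, state that the same structured adverse-event, abuse-indicator and suicidal-ideation questions are asked in both arms at the existing baseline and 3-month assessments. The 3-month questions should cover the whole period since baseline and be asked whatever the sessions have already found. Baseline answers help to separate existing problems from new ones. If the study manual or intake instrument already contains such questions, say so in section 10.
2. State in the SAP that any by-arm safety summary uses those answers, and that events found at sessions are listed separately as unequally ascertained.

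With two common queries per caregiver, k = 2 in both arms. At p = 0.2 detection from those queries is 1 - 0.8^2 = 0.36 in each, a ratio of 1, provided that caregivers disclose equally readily in both arms. Pooling session-detected events back in would restore the imbalance (5-8 versus 3 contacts, ratio 1.4-1.7 at p = 0.2), which is why they are kept apart.

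The cost is a few more questions at visits already planned and a line on reporting. The change does not equalise detection between visits, and it leaves the handling of a detected event as the protocol sets out.

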Discomfort due to the intervention: Even though this study builds on evidence-based strategies for support of family caregivers, subjects may experience discomfort or mild distress when discussing their caregiving experience or because of concerns about confidentiality. These risks are being minimized in several ways. First, caregiver will be given the option of discussing issues privately with the care manager during the intervention. Second, the care manager will be trained to monitor the nature of interactions between patients and family members and any serious issues that emerge will be discussed with the supervising team so that strategies can be developed to address any issues that arise. Finally, subjects will have the opportunity to drop out of the family-centered arm of the study and complete treatment by themselves or drop out of the study altogether.

Inconvenience due to questionnaires: To address the inconvenience associate with completing study questionnaires, we will give subjects the option of completing these in the home or by phone. In addition, during the consent process, participants will be advised that they can choose not to answer any questions that make them feel uncomfortable. Risks to subjects are minimal for several reasons.

This is a behavioral intervention and does not involve drug treatment. In prior studies conducted in the US with multi-cultural populations in the United States there have not been any serious adverse side events attributable to the intervention (personal communication with one of the PIs of a large-scale national study). It is also possible that elder/abuse or neglect may be detected during the study and require intervention. A protocol for handling cases of abuse/neglect according to local norms/resources has been developed in collaboration with our colleagues in Vietnam.

13) Potential Benefits to Subjects

There are several potential direct benefits to subjects. Subject may experience an increase in their knowledge and skills because of the intervention. In addition, caregivers will learn stress reduction techniques that may help reduce caregiving-related distress.

Participants will receive \$10 at the end of each study visit (including both intervention sessions and visits for administration of questionnaires).

Page 5 of 8 Revised: February 27, 2017

14) Multi-Site Research

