Study Title: Randomized controlled trial to test the feasibility, acceptability, and preliminary effectiveness of a psychosocial intervention to support Alzheimer's family caregivers in Vietnam.

NCT#: NCT03587974

Document Date: March 1, 2020

Document Type: Statistical Analysis Plan

Statistical Analysis Plan

Characteristics of the caregivers and the care recipients will be compared between the two groups using a two-sample t-test or Chi-square test; the Wilcoxon rank sum test or Fisher's exact test will be used if needed due to violations of the underlying assumptions. Primary analysis of the intervention effect will use an intent-to-treat approach, in which groups were compared based on randomization assignment. To account for the clustering of participants by commune, mixed effects models that included a cluster-specific random effect will be used to estimate differences between groups. Models will utilize the post-intervention assessment as the outcome and included the baseline assessment as a covariate. The post-intervention assessment will be divided by the standard deviation in the entire sample at baseline, so that interpretation of model coefficients will be in terms of standard deviation units. Model assumptions will be checked and met by the data. All analyses will be conducted in SAS, version 9.4, and a *p*-value less than 0.05 considered statistically significant.

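### Does the offer to destroy a withdrawing subject's records undermine the intention-to-treat comparison or the baseline scaling?

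*Protocol*

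**What the plan says.** Protocol section 11 reads: "Subjects (patients and family members) may withdraw at any time". It continues: "If they withdraw from the study, they will be given the option of having their records destroyed". Neither sentence defines the records or sets a last date for a request.

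Other places bear on the reach of the offer. Section 5 limits involvement: "Each family caregiver will participate in the study for 3 months". Section 9 sends copies abroad: "De-identified data will be transferred to UC Davis and the University of South Carolina electronically through an encrypted zip file". Sections 8 and 9 both have the key linking codes to persons destroyed once the study ends. Section 12 acknowledges that "subjects may experience discomfort or mild distress when discussing their caregiving experience or because of concerns about confidentiality". Section 4 plans 50 caregivers, 25 per arm.

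On analysis, the SAP states: "Primary analysis of the intervention effect will use an intent-to-treat approach, in which groups were compared based on randomization assignment". It also plans a between-group comparison of caregiver and care-recipient characteristics. The primary model is a mixed model for the post-intervention score, with the baseline score as covariate and a random effect for commune. The outcome is divided by the baseline SD of the whole sample. The SAP says nothing about withdrawn or erased records.

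**The concern.** An intention-to-treat analysis starts from everyone assigned, and erasure is one of the few events that can remove an assigned person from the dataset altogether. Ordinary dropout leaves the baseline score, the commune and the sessions attended. Erasure, read broadly, leaves nothing to describe and nothing from which to impute a missing 3-month score. Because subjects include both patients and family members, it is also unclear whether a patient's withdrawal reaches the caregiver's data.

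The trial is small and its aims include feasibility and acceptability, so who left, and after how many sessions, is part of what it sets out to learn. If several leavers chose erasure, the baseline table and the scaling SD would rest on fewer than 50 people, and the SAP plans no count that would show this.

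**Working it through.** There is no figure in the plan to reproduce: neither document gives a withdrawal rate, an SD or an intracluster correlation. The inputs from the documents are 50 caregivers, 25 per arm, and the SAP's model. The numbers erased and the gaps between leavers and stayers are assumptions.

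**Primary estimate.** The model needs a 3-month score. A leaver without one contributes nothing to the fit, so erasing that person's baseline record removes nothing from it. A completed 3-month score would be lost only if withdrawal were taken to continue after the final assessment. Section 5 makes that a strained reading, because participation lasts 3 months.

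**Coverage.** If 5 of 50 withdraw and 3 or 5 choose erasure, the table and SD rest on 50 − 3 = 47 or 50 − 5 = 45.

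**Baseline table.** If m of 25 in one arm are erased and lie a distance g from the rest, the arm mean moves by m × g / 25.

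- Low: 1 × 0.5 / 25 = 0.02 SD.
- High: 3 × 1.0 / 25 = 0.12 SD.
- Standard error of an arm difference, clustering ignored: √(2/25) = 0.283 SD. The high case is 0.12 / 0.283 = 0.42 of it. Positive clustering would enlarge the standard error and shrink that ratio.

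**Scaling SD.** Let a fraction p be erased, lying d stayer-SDs from the stayers, with equal spread in both groups. Then full SD / stayer SD = √(1 + p(1 − p)d²).

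| Erased | p | d | Ratio | A 0.50 SD effect reads |
|---|---|---|---|---|
| 1 of 50 | 0.02 | 0.5 | 1.002 | 0.501 |
| 3 of 50 | 0.06 | 1.0 | 1.028 | 0.514 |
| 5 of 50 | 0.10 | 0.5 | 1.011 | 0.506 |
| 10 of 50 | 0.20 | 1.0 | 1.077 | 0.539 |

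A simulation of 50 normal scores (40,000 replicates) brackets this. With 5 records removed at random, the ratio of the reduced SD to the full SD averages 1.00, with a 95% range of 0.916 to 1.046, so the SD can rise as well as fall. With the 5 highest scores removed, an extreme case, the SD falls to 0.85 of its full value and the coefficient reads about 18% larger.

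**Test.** Dividing the outcome by another constant divides the coefficient and its standard error alike, so the p-value stays put. A check on simulated data, using ordinary least squares without a cluster effect, gave coefficients of −0.201 and −0.235 under two scaling SDs and p = 0.297 under both.

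**Leavers against stayers.** The 95% half-width is t(0.975; k + 43) × √(1/k + 1/45), with k leavers kept and 45 stayers. It is 0.948 SD for k = 5 and 1.455 SD for k = 2. With all five kept, the comparison could still not resolve a difference of nearly one SD, and the SAP does not plan it.

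**The case for a change.** The best case for acting is that the remedy looks cheap. Defining the records and a cut-off, reporting by arm how many were randomised, withdrew and chose erasure, and stating the number behind the baseline SD would cost a few lines. Feasibility is a stated aim, and erasure cannot be undone. Participants too would benefit from knowing what the offer delivers once coded copies have left Vietnam.

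Part of this stands. The supplied text is silent on scope and timing, and the counts would make a report clearer. Three things weaken it as a reason to amend the plan.

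- The loss is conditional. Someone must withdraw, choose erasure, and have the offer read to cover coded analysis data. If transferred copies are not reached, the baseline data survive. The consent pages and the study manual are not supplied and may define the scope. Destruction of the linking key also bounds requests in practice, since a coded record can then no longer be traced through it, although it is not a stated deadline.
- The SAP's reference to the whole sample is naturally read as pooling the arms. It does not promise a baseline value from every person randomised. Likewise, comparing by assignment fixes the group in which a person is counted; it does not guarantee that the person's data exist.
- Nothing shows that assignment logs, withdrawal logs or filed safety reports would be erased, so the counts can be reported without new wording.

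A stronger remedy would keep coded data after withdrawal. That gives up a real protection among 50 caregivers in one area, where confidentiality is a named worry. It would also come late. The protocol says: "We will enroll subjects from April 1 through the end of September, 2018". Adding 3 months of participation takes the last assessment to about the end of December 2018, and the SAP is dated March 2020. Promises already made would have to be kept. A sensitivity analysis for missing 3-month scores answers a separate question: section 11 does not cause those scores to be missing, and erased records could not enter such an analysis.

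**Conclusion.** The silence in section 11 is real, but it calls for no change. The primary estimate is untouched for leavers without a 3-month score, and the p-value does not depend on the scaling SD. What remains is descriptive: a baseline mean shifted by 0.02 to 0.12 SD if 1 to 3 of 25 records in an arm go, and a 0.50 SD effect reading up to 0.51 with 1 to 3 of 50 erased or 0.54 with 10. These figures rest on assumed counts and on gaps of 0.5 to 1.0 SD between leavers and stayers. The extreme case of losing the five highest scores gives about 18% on the coefficient and still leaves the test alone.

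Offering erasure is a fair trade of some descriptive completeness for participant protection in a minimal-risk pilot. The remaining detail is a gap that analysts fill sensibly by giving the number of records behind the baseline table and the SD and accounting for withdrawals by arm. The conclusion would need another look only if erasure proved common or removed completed 3-month scores, and nothing in the documents points to either.
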